5.3.2 Safety Endpoints

Adverse events and adverse drug reactions

6. Target Sample Size and Term of the Study

6.1 Target Sample Size

30 subjects as investigational product vaccinated subjects

Rationale

The sample size was set at 30 subjects who are eligible for inclusion in a stratified analysis for exploring the causes of any differences that may be found in efficacy or safety between intramuscular administration (this study) and subcutaneous administration (study BK1310-J01), based on the sample size that was used in the intramuscular administration study that was conducted for the vaccine that has already been approved (VaxemHIB aqueous suspension for injection).

Additionally, a simulation found that the probability of a solicited adverse event that has an incidence of 5.8% occurring in a single subject if the sample size is 30 would be 83%. The figure of 5.8% was chosen because this was the incidence of the least frequently reported solicited adverse drug reaction in the BK1310 group in the Japanese phase 2 study of MT-2301 (study MT-2301-J01).

6.2 Study Period

June 2017 to October 2018 (registration deadline: July 2017)

7. Investigational Product

7.1 Names of the Investigational Products

Name: BK1310

Expected nonproprietary name: Adsorbed-purified pertussis/diphtheria/tetanus/inactivated polio (Sabin strain)/Haemophilus b (non-toxic mutant diphtheria toxin conjugate) combination vaccine

BK1310 is a syringe formulation that contains, in 0.5 mL, 10 µg of Hib antigen, in terms of the quantity of oligosaccharide, and that also contains the same antigen levels as those contained in TETRABIK.

7.2 Investigational Product Packaging and Labeling

(1) Packaging

Individual Cartons

Cartons containing the following investigational product

BK1310: 1 syringe

(2) Label

Both the individual cartons and the outer cartons will bear the following information.

- The fact that the contents are for use in a clinical study
- The name and address of the study sponsor
- The ID number
- The manufacturing number
- The storage method

More detailed information is provided in the "Investigational Product Control Procedures."

7.3 Storage Method

The investigational product should be stored shielded from light at not more than 10°C; it should not be allowed to freeze.

7.4 Investigational Product Handling, Storage, and Control

The study sponsor will deliver the investigational products once the contract with the study site has been concluded. The investigational product controller stored and controlled the investigational products and, after the conclusion of the study, will return all the unused investigational products and the empty outer cartons to the monitor according to the "Investigational Product Management Procedures" specified by the sponsor.

Furthermore, investigational product must not be used for any purpose other than those described in this study protocol (e.g., for other clinical studies, animal studies, basic research).

8. Subject Study Methods

8.1 Subject Screening and Preparation of an Enrollment Registry and ID Code List

The principal investigator will prepare a list of all subjects who have been screened (subjects whose legal guardians received an informed consent explanation), and will prepare a subject screening registry. The principal investigator will assign ID codes to subjects whose legal guardians have consented to have subjects participate in the study, and will prepare a subject ID code list. When doing so, the principal investigator will note the information that will serve as the key when referencing the subject's medical records (source documents).

The principal investigator will also prepare a subject registry that lists the sex, date of consent, subject ID codes, etc. of the subjects who have been enrolled in the study (including the subjects whose study treatments have been temporarily or permanently discontinued).

8.2 Enrollment of Subjects

Subjects will be selected in accordance with the procedures shown in Attachment 2, "Study Procedure Flow Chart."

The (sub)investigator will check to make sure that a subject who has consented to participate in the study meets the inclusion criteria and does not meet the exclusion criteria. The (sub)investigator will then judge as eligible for the study a subject for whom it has been determined, on the basis of a preliminary screening sheet on the day of the first vaccination of investigational product, that the subject can receive the investigational product, and from whom a blood sample has been collected prior to the first vaccination of the investigational product, and will record this subject in the source documents as a subject who has been enrolled in the study.

The (sub)investigator will prescribe the investigational product to the subject.

The investigational product controller will distribute the investigational product to the vaccinator. The vaccinator will administer the investigational product to the subject.

Test/Observation Parameters Required at Enrollment

Test and Observation Parameters	Description
Confirmation of inclusion/exclusion criteria	See "3.2 Inclusion Criteria" and "3.3 Exclusion Criteria"
Subject background investigation	Sex, date of birth (Western calendar), complications

8.3 Dose and Vaccination Method

8.3.1 Dose and Vaccination Method

The following investigational products will be administered.

BK1310: A single dose of 0.5 mL (that contains 10 µg of Hib antigen as the oligosaccharide)

For the primary immunization, subjects will receive 3 doses of investigational product intramuscularly (into the thigh), 0.5 mL for each dose, at intervals of 3 to 8 weeks (standard vaccination interval: 4 weeks). For the booster immunization, subjects will receive a single dose of investigational product intramuscularly (into the thigh) at 6 to 13 months after the primary immunization. However, the repeated vaccination with investigational product at the same location as that which was used for the previous dose will be avoided.

Rationale

These parameters were established in accordance with the "Immunization Guidelines."

The amount of Hib antigen in the investigational product has been set at 10 µg through a comprehensive determination made on the basis of, among other information, the results obtained after the administration of the third dose of the investigational product in Cohort 1 (after the completion of the primary immunization) in ongoing study BK1310-J01.

At present, overseas, most vaccines, except for live vaccines, are as a rule administered by intramuscular administration.¹⁶⁾ When multiple vaccines are administered simultaneously, or when many new vaccines are developed, particularly combined vaccines or vaccines with adjuvants, intramuscular administration is the standard administration method, in order to minimize local reactions. It has been reported that intramuscularly administered vaccines have the following features compared to subcutaneously administered ones.^{16),17),18)}

- Intramuscular administration results in fewer local reactions (redness, swelling, pain) than subcutaneous administration.
- Intramuscular administration affords a level of immunogenicity (e.g., an increase in the antibody titer) comparable to that afforded by subcutaneous administration.

Given these facts, the Japan Pediatric Society has requested that the intramuscular administration of inactivated vaccines be approved.¹³⁾ The applicant therefore designed this study to accompany development of subcutaneous administration (study BK1310-J01), which is currently underway. The objective of this study is to confirm the efficacy and safety in the clinical setting of the intramuscular administration of BK1310.

8.4 Treatment Period

Four doses administered over a minimum of 30 and a maximum of 68 weeks

Rationale

These parameters were established in accordance with the "Immunization Guidelines."

8.5 Concomitant Drugs/Therapies

8.5.1 Prohibited Concomitant Medication/Therapy

The concomitant use of the following drugs and therapies will be prohibited during the study periods (Visit 1 through Visit 6).

- (1) Hib, pertussis, diphtheria, tetanus, or polio vaccines other than the investigational products
- (2) Immunoglobulin preparations
- (3) Corticosteroids at prednisolone equivalent doses of 2 mg/kg/day or higher (except for topical drugs)
- (4) Immunosuppressants (except for topical drugs)
- (5) Blood transfusions
- (6) Immunosuppressant therapies
- (7) Investigational products other than BK1310

The concomitant use of the following drugs will be prohibited from 27 days before until 14 days after the vaccination with investigational product.

- (8) Live vaccines (e.g., BCG, measles, rubella, mumps, varicella, rotavirus*)

*: Simultaneous vaccination with the investigational product will be permitted only for a rotavirus vaccine

The concomitant use of the following drugs will be prohibited from 6 days before until 14 days after the vaccination with investigational product.

(9) Inactivated vaccines (e.g., Pneumococcal,** influenza, Japanese encephalitis, hepatitis A, hepatitis B**)

**: Simultaneous vaccination with the investigational product will be permitted only for the pneumococcal and hepatitis B vaccines. The site of vaccination will be the arm or the thigh on the side opposite that used to administer the investigational product.

Rationale

(1) This criterion was established because of the potential effects on the assessments of efficacy.

(2)(5) These criteria were established because of the potential effects on the assessments of efficacy, since they might contain antibodies to the active ingredients of the investigational drug.

(3)(4)(6) These criteria were established because of the potential effects on the assessments of efficacy and safety, since these drugs could suppress immune function.

(7) This criterion was established because of safety and ethics considerations.

(8)(9) These criteria were established because of safety and ethics considerations, in accordance with the vaccination intervals for other vaccines described in the Routine Immunization Guidelines. It was also decided that the concomitant use of other vaccines should be prohibited up until 14 days after vaccination with the investigational product in order to check the effects on safety of combining the vaccines.

8.5.2 Records of Concomitant Drugs and Therapies

The (sub)investigator will record in the “Concomitant Drugs” and “Concomitant Therapies” columns of the case report form the following information about all drugs and therapies used concomitantly during the period from Visit 1 to Visit 4 and during the period from Visit 5 to Visit 6. However, saline solutions and similar products used to dissolve injectable products will not be recorded.

- Concomitant drugs: Drug name, daily dose,* route of administration, treatment period, objective of use
- Concomitant therapies: Therapy name, duration, objective of use

*: This information will be recorded only for corticosteroids (except for topical agents).

In addition, if a prohibited concomitant drug was used during the period from Visit 4 to Visit 5, then this will be recorded in the specified column of the case report form.

8.6 Subject Management

(1) Lifestyle Guidance

The (sub)investigator or a clinical research coordinator will provide lifestyle guidance to the legal guardian and request that they comply with the following rules.

- 1) Subjects are expected to undergo the observations/tests on the specified days. If a subject cannot come in to the study site on the specified day, the legal guardian must notify the (sub)investigator or a clinical research coordinator and follow his or her instructions.
- 2) The legal guardian must carry around a clinical study participation card and present it when the subject is examined at another hospital or department. In addition, if the subject uses any drugs that have been prescribed by a doctor outside of this study, or even any drugs that have been purchased by the legal guardian at a drug store, the legal guardian must be sure to inform the (sub)investigator or a

clinical research coordinator. Also, if the subject is going to use a new drug during the study, the legal guardian must notify the (sub)investigator or a clinical research coordinator in advance.

- 3) In order to be able to respond to emergency symptoms, such as anaphylaxis, during the 30 minutes after vaccination with the investigational product, the subject will for this period remain in a location within the hospital that can be immediately contacted by the (sub)investigator.
- 4) If the subject develops any abnormalities, or if the subject's condition seems to be different from normal, then the (sub)investigator must be contacted.
- 5) Following vaccination, the site of vaccination must be kept clean.
- 6) During the term of the study, and particularly until 14 days after vaccination, the legal guardian must take care for the subject to avoid undue physical or mental burdening situations.

(2) Instructions for Entering Information in the e-Diary

The (sub)investigator or a clinical research coordinator will instruct the legal guardian to enter in the e-Diary information about the parameters specified in Section 9.2.4.1 every day up through Day 14 after vaccination with the investigational product. If the subject's symptoms do not return to normal by Day 14 after vaccination with the investigational product then, as a rule, the legal guardian will be instructed to enter information about them in the e-Diary until they return to normal. In this case, the legal guardian will be instructed not to forget to take the subject's body temperature (e.g., by deciding in advance on a set time for measuring body temperature).

1) Measurement of body temperature

The subject's legal guardian will measure the subject's axillary body temperature, and enter the result in the e-Diary. If the subject's temperature is measured twice in 1 day because of, for example, a pyrexia, then the highest reading will be entered.

2) Observation of symptoms

The legal guardian will monitor the subject's vaccination site reactions as well as any reactions other than vaccination site reactions (systemic reactions), and enter them in the e-Diary. When doing so, the legal guardian will also enter into the e-Diary the long axis for any redness, swelling, or induration at the vaccination site.

Furthermore, if the subject is examined or treated at another medical institution or by another treating department, the details thereof will be explained to the (sub)investigator or a clinical research coordinator.

9. Tests/Observations

9.1 Test/Observation Schedule

	Day of consent	Visit 1		Visit 2		Visit 3		Visit 4		Visit 5		Visit 6 At discontinuation	
		1st vaccination		2nd vaccination		3rd vaccination		Post-vaccination Examination 1		4th vaccination			
		Before	Vaccination	Before	Vaccination	Before	Vaccination	After	After	Before	Vaccination		
Allowable Window		D1		Visit 1 + 3 - 8 weeks		Visit 2 + 3 - 8 weeks		Visit 3 + 4 - 6 weeks		Visit 3 + 6 - 13 months		Visit 5 + 4 - 6 weeks	
Written informed consent	•												
Investigation of subject background	•									•			
Examination	•		• ¹	•		• ¹	•	• ¹	•	•	• ¹	•	
Body temperature measurement (axillary)	•			•			•			•			
Investigational product vaccination		•			•			•			•		
Blood sampling (antibody titer)	•								•	•		• ²	
Adverse events ³		←		→									
e-Diary ⁴			•			•			•		•		

*1: Subjects will be asked to wait in the hospital for 30 minutes after receiving the investigational product, and will be examined 30 minutes after vaccination.

*2: Blood samples will be collected for antibody titer measurement only at discontinuation after the third or fourth dose of the investigational product has been administered.

*3: An investigation will be performed to confirm whether or not the subject experienced any adverse events during the period from Visit 1 to Visit 4, and during the period from Visit 5 to Visit 6, based on examination of the subject at the study visits and based on the subject's e-Diary. Only serious adverse events will be investigated during the period from Visit 4 to Visit 5.

*4: Every day until 14 days after each dose, if the subject's symptoms have not returned to normal by Day 14 after vaccination with the investigational product, then the legal guardian will be asked to, as a rule, fill out the e-Diary until the symptoms return to normal.

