The period from the first vaccination with the investigational product until Post-vaccination Examination 2 will be considered the safety assessment period. However, the collection of all adverse events will be performed for the period from the first vaccination with the investigational product until Post-vaccination Examination 1, and also for the period from the vaccination of the fourth dose of the investigational product until Post-vaccination Examination 2. Additionally, information about serious adverse events will be collected throughout the entire safety assessment period.

(4) Adverse event assessment and criteria

1) Day of onset

The day of onset will be the day on which the symptom is observed or the day on which the clinical test value abnormality was observed.

2) Severity

Adverse event severity will be classified using the following categories.

Event	Mild	Moderate	Severe
Vaccination site redness	long axis \leq 2.0 cm	long axis $>$ 2.0 cm, \leq 5.0 cm	long axis $>$ 5.0 cm
Vaccination site swelling			
Vaccination site induration			
Administration site pain	Whimpers when the vaccination site is touched	Cries when the vaccination site is touched	Cries when vaccinated leg is moved
Pyrexia	$\geq 37.5^{\circ}\text{C}$, $< 38.5^{\circ}\text{C}$	$\geq 38.5^{\circ}\text{C}$, $< 40.0^{\circ}\text{C}$	$\geq 40.0^{\circ}\text{C}$
Decreased appetite	A little decreased	Half or less of normal	Hardly eats at all

Adverse event severity other than that described above will be classified using the following categories.

1. Mild: No effect on the subject's activities of daily living
2. Moderate: The event impacts the subject's activities of daily living
3. Severe: The event prevents the subject from performing activities of daily living

3) Seriousness

The seriousness of adverse events will be classified using the following categories.

1. Not serious: Anything other than 2 below
2. Serious: Any of a) through f) below
 - a) Death
 - b) A life-threatening event
 - c) Necessitates admission to a hospital or clinic for treatment, or the prolongation of a hospital stay
 - d) Disability
 - e) A serious outcome comparable to those listed in a) through d) above
 - f) Congenital disease or abnormality in the next generation

4) Causal relationship to the investigational product

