12.1 Subject Discontinuation Criteria

If any of the following discontinuation criteria are met, the subject will be discontinued from the study.

- (1) If the legal guardian requests discontinuation.
- (2) If it is determined that the subject is clearly ineligible to participate in the study.
- (3) If the (sub)investigator determines that it would be difficult for the subject to continue the study because of the emergence of, for example, an adverse event.
- (4) If the (sub)investigator determines that the subject should be discontinued from the study for some other reason.

Rationale

These criteria were established to allow the study to be ethically conducted and in consideration of subject safety.

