12.2 Discontinuation Procedures

If a subject is discontinued from the study during the term of the study, the (sub)investigator will take whatever actions are appropriate for the subject, and will inform the monitor in question that the subject has been discontinued from the study.

The day of study discontinuation will be the day on which the (sub)investigator made the decision to discontinue the subject from the study.

The (sub)investigator will perform follow-up by examining the subject as much as possible to investigate the presence or absence of adverse events in the 2 weeks after vaccination with the investigational product (in the period up until the day of discontinuation if the day of discontinuation is more than 2 weeks after vaccination with the investigational product). If the subject is discontinued from the study after the third or fourth dose (except for subjects discontinued in the period from after Post-vaccination Examination 1 to before the fourth vaccination), blood samples for antibody titer measurement will be collected whenever possible 4 to 6 weeks after vaccination. If a subject has not completed all of the vaccinations, the subject's legal guardian will be given a full explanation of the vaccinations that the subject will receive after the subject has been discontinued from the study.

The concomitant medications will be confirmed at discontinuation, at the time of blood sample collection, or at 2 weeks after vaccination, whichever comes last.

The (sub)investigator will record the day of discontinuation and the reason for discontinuation* in the case report form.

For subjects for whom the specified observations/tests cannot be performed at discontinuation, or who did not come in for any study visits after discontinuation, the reasons for this, the subject's subsequent course, etc. will be followed up either in writing (correspondence) or by telephone or the like.

If the subject does not come in for a visit, the (sub)investigator or a clinical research coordinator will ask the subject's guardian to fill out the e-Diary as much as possible.

*: The "reason for discontinuation" will be selected from among the following.

1. Adverse event
2. Death
3. Clearly unsuitable as a subject for the study

4. Study protocol deviation
5. Technical problem
6. Subject's legal guardian requested discontinuation

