7.6.1.1. Adverse Event Incidences

Analysis population(s): Safety analysis set

Analysis parameter: Adverse events (solicited adverse events, immediate reactions, other), adverse drug reactions (solicited adverse events, immediate reactions, other), serious adverse events, serious adverse drug reactions, adverse events leading to discontinuation, adverse drug reactions leading to discontinuation

Analysis method: The number and proportion (and 95% confidence interval thereof) of subjects experiencing each type of event will be calculated.

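### Two adverse event collection rules conflict for a child who stops between Visit 4 and Visit 5, so a non-serious event that ends the series may not reach the discontinuation tables

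*Protocol*

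**What the plan says.** The limit on collection appears in several places. Footnote *3 of the visit schedule (Protocol synopsis, Protocol 9.1 and SAP 2.3) says "Only serious adverse events will be investigated during the period from Visit 4 to Visit 5". Protocol 9.2.4.2(3) agrees: "the collection of all adverse events will be performed for the period from the first vaccination with the investigational product until Post-vaccination Examination 1", and again from the fourth dose to Post-vaccination Examination 2. Outside those two windows, "information about serious adverse events will be collected throughout the entire safety assessment period". The follow-up rule in 9.2.4.2(7) mentions only serious events for the gap.

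The rules for discontinuation are wider. Protocol 12.1(3) allows a child to be stopped when the investigator finds it "difficult for the subject to continue the study because of the emergence of, for example, an adverse event", with no requirement that the event be serious. Protocol 12.2 then asks the investigator to look for adverse events after the dose, or "in the period up until the day of discontinuation if the day of discontinuation is more than 2 weeks after vaccination". It adds: "The (sub)investigator will record the day of discontinuation and the reason for discontinuation* in the case report form". Adverse event is the first reason on the list.

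On the analysis side, SAP 7.6.1.1 plans numbers, proportions and 95% confidence intervals for "adverse events leading to discontinuation, adverse drug reactions leading to discontinuation". SAP 7.6.1.2 and Tables 14.3.1.6 and 14.3.1.7 break these down by term. None is restricted by seriousness or period. SAP 7.2.2 counts reasons for discontinuation separately.

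**The concern.** The same child in the same period falls under two rules with different scope, and the documents do not say which governs. Each choice has a cost.

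- A site that takes the footnote literally opens no event record for a non-serious event in the gap, even one that ends the vaccine series. The disposition table would then show a withdrawal for an adverse event while the safety tables show none.
- A site that follows 12.2 records non-serious gap events for withdrawn children, but nobody records them for children who go on to dose 4. The SAP has no rule that separates these events, so the overall incidence would rest on unequal observation.

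Safety of the intramuscular route is a stated objective, and events that stop the series are a planned output. With several sites, the data could mix the two practices.

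**Working it through.** The plan gives no figure for this point. Its one design calculation, an 83% chance of seeing an event of 5.8% incidence in 30 subjects, reproduces as 1 − 0.942^30 = 83.3% (at least one subject). Nothing below depends on it.

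**Do both rules reach the same child?** Visit 4 falls 4 to 6 weeks after Visit 3 (Protocol 9.1). A child stopped after an in-window Visit 4 and before dose 4 is therefore at least 4 weeks past the third dose. That exceeds the 2 weeks named in 12.2, so the search there runs to the day of discontinuation and covers the gap. Only events with onset in the gap are affected. An event that began before Visit 4 already has a record.

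**Does 12.2 exempt this group?** The same paragraph names children who stop between Post-vaccination Examination 1 and dose 4, and exempts them from blood sampling only. It makes no exception for adverse events.

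**Length of the gap.** Inputs: Visit 4 at Visit 3 plus 4 to 6 weeks, Visit 5 at Visit 3 plus 6 to 13 months, and 1 month = 365.25/12/7 = 4.348 weeks.

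- Shortest: 6 × 4.348 − 6 = 20.1 weeks.
- Longest: 13 × 4.348 − 4 = 52.5 weeks.

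**Share of Visit 1 to Visit 6.** The span is the two primary intervals (3 to 8 weeks each), plus Visit 3 to Visit 5, plus 4 to 6 weeks to Visit 6.

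- Lowest: 20.1 / (8 + 8 + 26.1 + 6) = 20.1/48.1 = 42%.
- Highest: 52.5 / (3 + 3 + 56.5 + 4) = 52.5/66.5 = 79%.

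**Effect of one lost stopping event.** Assume that all 30 children are in the safety set, that one stops for a non-serious gap event, and that the event is not recorded. The intervals are Clopper-Pearson (SAP 7.1.3).

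- True: 1/30 = 3.3%; lower limit 1 − 0.975^(1/30) = 0.1%; upper limit, the 97.5th percentile of Beta(2, 29), = 17.2%.
- Printed: 0/30 = 0%; upper limit 1 − 0.025^(1/30) = 11.6%.

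**Effect of following 12.2.** SAP 7.6.1.1 counts subjects. The overall row therefore rises by 1/30 = 3.3 percentage points only for a withdrawn child whose sole recorded events fall in the gap. Rows for individual terms can rise by one for each new term.

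**The case against.** The best reply is that the documents can be read together: a general schedule rule, plus a specific rule for withdrawals. A reader might infer from the footnote that a non-serious stopping event must be missing from the discontinuation tables. The documents do not support that. A child stopped by an event is a discontinued child, and 12.2 applies to exactly that child. Protocol 9.2.4.2(5) has event details recorded, including the action taken with the product. The reason goes into the case report form, and the SAP tables accept events of any seriousness from any period. Loss requires a site to apply the footnote and overlook 12.2, or the follow-up in 12.2, which is worded as best effort, to fail.

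A reader might also infer that 12.2 would fill the overall incidence with months of childhood illness. That is conjecture. It concerns only the few of 30 children who leave in the gap. The daily diary normally ends 14 days after a dose. Gap events would fall in the residual category of SAP 7.6.1.2, apart from solicited and immediate reactions, and could be identified from the days since the preceding dose derived in SAP 4.1(3).

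Both replies stand as limits on size. Neither removes the conflict: the footnote says that only serious events are investigated, no cross-reference tells a site that 12.2 is an exception, and the SAP does not say how the resulting events are counted.

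**Conclusion.** The conflict is real and the passages must be reconciled. The supportable conclusion is conditional: a non-serious event that stops a child in the gap may be absent from Tables 14.3.1.6 and 14.3.1.7, depending on which section the site follows. If 12.2 is followed, the overall incidence is slightly uneven between withdrawn and continuing children.

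The gap is long (42% to 79% of Visit 1 to Visit 6), but the number of children affected is probably small and the documents give no rate. The contrast of 1/30 with 0/30 assumes both the event and its loss, so it is an illustration and not an expected undercount. The study is exploratory with no tests, and no sample size or error rate changes. This is a minor point, worth fixing because a planned safety output depends on it and the fix is cheap.

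**What to change.** - **Footnote *3 (Protocol synopsis, Protocol 9.1, SAP 2.3) and Protocol 9.2.4.2(3):** state that between Visit 4 and Visit 5 serious adverse events, and any adverse event that leads to discontinuation, are collected. Add a cross-reference to 12.2.
- **Protocol 12.2:** leave the collection as it is. Narrowing it to match the footnote would make the rules uniform but would discard safety data.
- **SAP 7.6.1:** state that other non-serious events with onset between Visit 4 and Visit 5 are listed and not counted in the overall incidence. Listing 16.2.5.1 can carry them.
- **Before database lock:** check that every disposition reason of adverse event has a matching event record.

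The cost is a few one-sentence edits, one data check, and at most one extra event form per affected child. The discontinuation table may look slightly less favourable.
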